1.5.1. Hepatic Injury

A number of on-going or completed clinical trials with AAV-based vectors have demonstrated the relative safety of this approach to treat various diseases such as hemophilia, spinal muscular atrophy (SMA) and other genetic disorders. The most consistent treatment-emergent adverse reaction has been elevations in liver enzymes, mostly related to high (>1E+12 vg/kg) vector doses. The timing of the asymptomatic liver enzyme elevations post-gene transfer has varied, but most have been adequately treated with the addition of corticosteroids with no impact on transgene expression. Additionally, subjects treated with AAV-based vectors typically generate an immune response to the AAV capsid and may develop a cellular response to the transgene. In an attempt to reduce any inflammatory and immune responses to the vector, subjects in an ongoing trial are now receiving steroids for several weeks after vector delivery.

To address the shortcoming of the standard paradigm for monitoring of liver health in DMD patients, glutamate dehydrogenase (GLDH) has been identified as a liver-specific biomarker of liver injury that is independent of muscle damage.⁵⁰ In these studies, GLDH has been found to be as effective as ALT in diagnosing liver injury. Thus, GLDH will be used as a sensitive biomarker of liver injury in this study and may be used to guide additional

immunomodulatory intervention, as well as to confirm potential cases meeting Hy's law criteria based on elevations of bilirubin alone (in the context of elevated AST/ALT due to muscle damage).

As with other gene therapy clinical studies, elevations in liver enzymes are not unexpected. In this study, all subjects will have received glucocorticoids for at least 6 months, with a stable daily regimen for at least 3 months prior to the Baseline visit, and will continue to receive elevated daily doses of glucocorticoids for at least 3 months post-infusion of investigational product before returning to their pre-study doses of glucocorticoids for at least the remainder of the first year post-infusion. It is anticipated that the pre-existing steroid regimen along with the 3-month modified regimen may assist in controlling potential AAV-mediated liver injury. However, should liver injury be detected, the glucocorticoid doses may need to be increased further, or other immunomodulatory therapy initiated, in consultation with the assigned immunopharmacologic and/or hepatic experts.

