8.4.2. Potential Cases of Drug-Induced Liver Injury

Humans exposed to a drug who show no sign of liver injury (as determined by elevations in transaminases) are termed "tolerators," while those who show transient liver injury, but adapt are termed "adaptors." In some subjects, transaminase elevations are a harbinger of a more serious potential outcome. These subjects fail to adapt and therefore are "susceptible" to progressive and serious liver injury, commonly referred to as drug-induced liver injury (DILI).

In the majority of DILI cases, elevations in aspartate aminotransferase (AST) and/or alanine aminotransferase (ALT) precede total bilirubin (TBili) elevations (>2 × ULN) by several days or weeks. The increase in TBili typically occurs while AST/ALT is/are still elevated above 3 × ULN (ie, AST/ALT and TBili values will be elevated within the same lab sample). In rare instances, by the time TBili elevations are detected, AST/ALT values might have decreased. This occurrence is still regarded as a potential DILI. Therefore, abnormal elevations in either AST OR ALT in addition to TBili that meet the criteria outlined below are considered potential DILI (assessed per Hy's law criteria) cases and should always be considered important medical events, even before all other possible causes of liver injury have been excluded.

The threshold of laboratory abnormalities for a potential DILI case depends on the subject's individual baseline values and underlying conditions. Subjects who present with the following laboratory abnormalities should be evaluated further as potential DILI (Hy's law) cases to definitively determine the etiology of the abnormal laboratory values:

- Subjects with AST/ALT and TBili baseline values within the normal range who subsequently present with AST OR ALT values >3 × ULN AND a TBili value >2 × ULN with no evidence of hemolysis and an alkaline phosphatase value <2 × ULN or not available.
- For subjects with baseline AST **OR** ALT **OR** TBili values above the ULN, the following threshold values are used in the definition mentioned above, as needed, depending on which values are above the ULN at baseline:
 - Preexisting AST or ALT baseline values above the normal range: AST or ALT values >2 times the baseline values AND >3 × ULN; or >8 × ULN (whichever is smaller).

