 - Preexisting values of TBili above the normal range: TBili level increased from baseline value by an amount of at least 1 × ULN **or** if the value reaches >3 × ULN (whichever is smaller).

Rises in AST/ALT and TBili separated by more than a few weeks should be assessed individually based on clinical judgment; any case where uncertainty remains as to whether it represents a potential Hy's law case should be reviewed with the sponsor.

In addition, however, as described in Section 1.5.1, in DMD patients, the standard biomarkers of the onset of hepatocellular injury such as ALT and AST are not capable of detection of liver damage due to the release of these enzymes from diseased skeletal muscle. To address the shortcoming, elevations of GLDH >2 x ULN will also be assessed individually based on clinical judgment and with the support of the *ad hoc* hepatic and/or immunopharmacologic expert (s) supporting the E-DMC; any case where uncertainty remains as to whether it represents a potential Hy's law case should be reviewed with the sponsor. Subjects who experience a consistent GLDH elevation above 3 × ULN may also be monitored more frequently to determine if they are an "adaptor" or are "susceptible", as defined above.

If any of the above criteria is met, the subject should return to the investigator site and be evaluated as soon as possible, preferably within 48 hours from awareness of the abnormal results. This evaluation should include laboratory tests, detailed history, and physical assessment.

In addition to repeating measurements of AST and ALT and TBili, laboratory tests should include albumin, creatine kinase (CK), direct and indirect bilirubin, gamma-glutamyl transferase (GGT), GLDH, prothrombin time (PT)/international normalized ratio (INR), total bile acids, alkaline phosphatase and acetaminophen drug and/or protein adduct levels.

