Analysis windows for these summaries and graphical displays by visit are provided in Appendix 2.

Hepatotoxicity evaluation:

To assess potential liver injury, the eDISH plot will be used to present the liver safety data (Watkins et al., 2011⁷). Specifically, the peak AST or ALT (x-axis) and peak TBili (y-axis) will be shown as multiples of (x-fold or y-fold) the ULN on log scales displayed for each participant within a specific timeframe (week 52 for primary safety analyses). Four quadrants defined by the two lines corresponding to 3×ULN for peak AST or ALT and 2×ULN for peak TBili will be shown.

A separate listing displaying the following parameters over time will be generated for participants located in the right upper quadrant.

• ALT, AST, ALP, TBili, GGT, GLDH, CK, creatine kinase myocardial b fraction, platelets, Hepatitis A virus antibody and immunoglobulin M antibody, Hepatitis B virus surface antigen, Hepatitis C virus antibody, and Hy's Law criteria.

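### The SAP's liver plot uses AST/ALT, which muscle release confounds in DMD; GLDH needs its own plot against bilirubin and its own listing trigger

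*SAP*

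**What the plan says.** **The display.** Under the hepatotoxicity evaluation in SAP 6.1.2, "the peak AST or ALT (x-axis) and peak TBili (y-axis) will be shown as multiples of" ULN, on log scales, for each participant. "Four quadrants defined by the two lines corresponding to 3×ULN for peak AST or ALT and 2×ULN for peak TBili will be shown". The 3×ULN line is fixed, with no adjustment for baseline.

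**The follow-up.** "A separate listing displaying the following parameters over time will be generated for participants located in the right upper quadrant". The listed parameters begin "ALT, AST, ALP, TBili, GGT, GLDH, CK, creatine kinase myocardial b fraction, platelets" and go on to hepatitis serology and the Hy's law criteria.

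**GLDH elsewhere in the SAP.** Section 3.1.2 has GLDH summarized to monitor liver toxicity. The parameter table in 6.1.2 gives it change and percent change by visit, a shift table (<LLN, Normal, >ULN) and a box plot of changes.

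**The protocol on AST and ALT.** Section 8.4.2 says that in DMD "the standard biomarkers of the onset of hepatocellular injury such as ALT and AST are not capable of detection of liver damage", because diseased skeletal muscle releases these enzymes. For a raised baseline it sets an adjusted threshold, "AST or ALT values >2 times the baseline values AND >3 × ULN; or >8 × ULN", whichever is smaller.

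**The protocol on GLDH.** Section 1.5.1 says "GLDH will be used as a sensitive biomarker of liver injury in this study". Section 8.4.2 has GLDH above 2×ULN assessed individually, and says that consistent elevation above 3×ULN may lead to more frequent monitoring.

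**The concern.** The SAP's only display that combines liver markers within a participant puts on its horizontal axis two enzymes that the protocol says cannot detect liver damage in these patients. The marker chosen to replace them is on neither axis, and it does not decide who is listed.

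Hepatic injury is the first risk discussed in Protocol 1.5, and the incidence and magnitude of abnormal laboratory findings is a primary endpoint. At stake is whether the report lets a reader find participants whose GLDH rose without bilirubin passing 2×ULN. Such cases are plausible here: the Amendment 7 rationale in Protocol Appendix 3 records that the E-DMC had reviewed three cases of elevated GLDH. It gives neither their levels nor the bilirubin values that went with them.

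**Working it through.** The documents state no figure for how well the plot discriminates, so there is none to reproduce. The checks apply the SAP's rules to the protocol's thresholds.

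**1. Who enters the liver listing.** The SAP's rule is AST/ALT >3×ULN and TBili >2×ULN. For a participant with GLDH >2×ULN, the four possible positions are:

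| TBili >2×ULN | AST/ALT >3×ULN | In liver listing |
|---|---|---|
| no | no | no |
| no | yes | no |
| yes | no | no |
| yes | yes | yes |

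Only one of the four leads to the listing. GLDH plays no part in the rule: with GLDH at or below 2×ULN the last column is the same. These are positions, not expected counts of participants.

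**2. What the GLDH shift table can show.** Exclusion criterion 9f in Protocol 4.2 rules out screening GLDH above 2×ULN, so values between 1× and 2×ULN can be enrolled. The top category of the shift table is >ULN. A participant going from 1.5×ULN to 10×ULN is >ULN before and >ULN after, so no shift is recorded. The change table and box plot reflect the size of such a rise within the cohort distribution, but they mark neither 2×ULN nor 3×ULN and do not show that participant's bilirubin.

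**3. What the left/right split is worth.** The documents give no AST/ALT distribution, so this is an illustration on assumed inputs. Let q be the share of participants whose peak AST/ALT exceeds 3×ULN from muscle alone. Let s = 0.9 be the chance that liver injury alone would cross that line, independently of muscle. The likelihood ratio for lying right of the line is LR+ = [1 − (1 − q)(1 − s)] / q. With 22 treated participants (SAP 2.5):

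| q | Right of the line without liver injury (22 × q) | LR+ |
|---|---|---|
| 0.50 | 11.0 | 0.950 / 0.50 = 1.90 |
| 0.80 | 17.6 | 0.980 / 0.80 = 1.225 |
| 0.95 | 20.9 | 0.995 / 0.95 = 1.05 |
| 1.00 | 22.0 | 1.000 / 1.00 = 1.00 |

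The more common muscle-derived elevation is, the less the split says about the liver. At q = 1 only the TBili line carries information.

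**4. Whether the flat 3×ULN line loses cases.** Take the criteria of Protocol 8.4.2 in turn.
- Normal baseline: AST or ALT >3×ULN with TBili >2×ULN. This is the upper right quadrant.
- Raised AST/ALT baseline: both routes, >2× baseline and >3×ULN, or >8×ULN, exceed 3×ULN.
- Raised TBili baseline: a rise of at least 1×ULN from a value above 1×ULN gives more than 2×ULN. The alternative, >3×ULN, does so as well.

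Every such case falls in the upper right quadrant. Using separate peaks makes the quadrant wider still, because the two peaks need not coincide. The quadrant also leaves out the protocol's hemolysis and alkaline phosphatase conditions. It is therefore less specific than the protocol's definition, but no less sensitive.

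**The case against.** The strongest reply is that the plot and its listing already follow the protocol. Section 1.5.1 has GLDH confirm potential Hy's law cases that rest on "elevations of bilirubin alone (in the context of elevated AST/ALT due to muscle damage"). A TBili line at 2×ULN, followed by a listing that sets GLDH and GGT beside CK, is that sequence. **This stands** for participants whose TBili exceeds 2×ULN, and it is the reason to keep the existing plot.

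A second reply is that GLDH-only elevations are reported elsewhere. GLDH has its own by-visit outputs. SAP 6.1.2 also lists laboratory data without a quadrant condition, although it names hematology, chemistry and urinalysis while Protocol Table 1 places GLDH under Other. Protocol 8.4.2 has GLDH above 2×ULN assessed during the study, and findings that need further testing become adverse events under 8.2.2. **This stands in part.** Such cases can appear in the report, but none of these outputs picks them out by the protocol's GLDH levels or sets them beside bilirubin.

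A third reply is that this is a descriptive display in a study without formal hypothesis testing. **That is correct**, and it limits the weight of the point.

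A reader might go further and infer that the SAP leaves GLDH out of the liver evaluation, that all four quadrants are uninformative, that the flat line misses Hy's law cases, or that GLDH-only cases are never listed at all. The documents support none of these. GLDH is in the quadrant listing and has its own summaries; the bilirubin axis carries information; step 4 of the working shows that no such case is lost; and the general laboratory listing has no quadrant condition. What holds is that these cases never enter the liver-case listing.

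**Conclusion.** The concern holds in a limited form. The horizontal axis of the eDISH plot is confounded by muscle release, on the protocol's own account, so the left/right split cannot separate liver from muscle injury. At participant level GLDH enters the liver evaluation only after TBili exceeds 2×ULN, with AST/ALT also above 3×ULN. The GLDH shift table stops at >ULN, and no specified output shows the protocol's 2× or 3×ULN levels or pairs GLDH with bilirubin.

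The number of participants affected cannot be derived from the documents. The likelihood ratios, 1.90 falling to 1.00 as q goes from 0.50 to 1.00, rest on the assumed q and s and show direction only. The listing and shift-table findings follow from the text and need no assumption. No sample size, estimate or error rate is affected. This is a cheap improvement to the reporting of a named risk, not a defect that undermines the safety analysis.

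**What to change.** In SAP 6.1.2:

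- Keep the eDISH plot as it is.
- Add a companion plot, one point per participant, of peak GLDH/ULN against peak TBili/ULN on log scales. Draw reference lines at 2× and 3×ULN for GLDH and at 2×ULN for TBili, all levels that the protocol already uses.
- Extend the over-time liver listing to any participant with post-baseline GLDH above 2×ULN, in addition to those in the upper right quadrant.
- Optionally, mark the AST/ALT points that meet the baseline-adjusted threshold of Protocol 8.4.2. This adds specificity but catches no further case.

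The cost is SAP wording, one figure and a longer listing. GLDH and bilirubin are already collected, and no clinical rule or study procedure changes.

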6.1.3. Vital Signs

Absolute values and changes from baseline in systolic and diastolic blood pressure, respiratory rate and pulse rate will be summarized by dose cohort, ambulatory status at baseline, and study visit. Tables will be paged by parameter. Baseline is as defined in Section 3.1.3.

The maximum increase from baseline for systolic, diastolic blood pressures and pulse rate will be calculated by first subtracting the baseline value from each post-dose measurement to give the change from baseline. The maximum of these values over the respective period will then be selected, except in the case where a participant does not show an increase. In such an instance, the minimum decrease should be taken.

Similarly, the maximum decrease from baseline for systolic, diastolic blood pressures and pulse rate will be determined by selecting the minimum value of the changes from baseline. In cases where a participant does not show a decrease, the minimum increase should be taken.

Maximum increases and decreases in vital signs will be summarized by dose cohort and ambulatory status at baseline.

Categorical tables (including post-baseline values, maximum increases, and maximum decreases) will also be provided for the first 7 days of follow-up and the first 30 days of follow-up.

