9.2.1. Derivation of Vital Signs Parameters

Blood pressures and heart rate will be recorded at each assessment time indicated in the Schedule of Activities. Baseline for vital signs will be defined as the last measurement before the Day 1 investigational product administration.

Vital signs (BP; HR) will be assessed for clinically relevant trends. The standard algorithms and reporting formats will be applied for analyzing all safety data.

Absolute values and changes from baseline for systolic and diastolic blood pressure and heart rate will be summarized by dose level, ambulatory status at baseline and study visit.

Maximum absolute values and maximum changes from baseline for vital signs will also be summarized descriptively by dose level and ambulatory status at baseline using categories as defined in the SAP. Numbers and percentages of subjects meeting the categorical criteria will be provided and individual values listed in the study report.

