Section 5.3.5 and Appendix 2: Revised to include the worst value if multiple values are observed within a
window.
Section 5.3.6 and 6.3.2.2: Moved all analyses to assess
· · · · · · · · · · · · · · · · · · ·
the impact of the COVID-19 pandemic to a supplementary SAP.
Section 6.1.2. Clarified that if there is a local and
central laboratory collection on the same day, the
central laboratory value will be used for analysis. Removed summary of change from baseline to last
observation in laboratory tests. Clarified that
externally normalized values will be normalized to
pediatric textbook ranges. Added content related to
cTn-I analyses.
Section 6.1.3: Added categorical tables for the first 7
days of follow-up and the first 30 days of follow-up.
Section 6.1.4: Removed listing.
Section 6.1.5: Removed summaries of physical exam and neurological exam since any significant findings
are recorded as AEs.
Section 6.3.2.1: Added a sentence to set the total score
to missing if one or more of the 17 items of NSAA is
missing. Clarified the definition of skills gained and
added definitions for rise from floor velocity and 10
meter run/walk velocity.
Section 6.4.2: Added age subgroups
Section 6.5.1: Removed ventilatory support.
Section 6.4.3: Removed reference to flagging specific
mutations in the listing.
Section 8: Moved references to endnotes.
Throughout the SAP: Changed PF-06939926 to
fordadistrogene movaparvovec.
Throughout SAP: Removed refence to sponsor
reporting standards.

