3. ENDPOINTS AND BASELINE VARIABLES: DEFINITIONS

3.1. Primary Endpoints

- Incidence of both dose-limiting and treatment-related AEs, inclusive of infusion and injection site reactions, through 1 year post-treatment.
- *Incidence, severity, and causal relationship of TEAEs through 1 year posttreatment.*
- Incidence and magnitude of abnormal laboratory findings through 1 year posttreatment.
- Abnormal and clinically relevant changes in physical and neurological examinations, weight, vital signs, ECG, cardiac MRI (or echocardiogram-) measured LVEF, CSSRS through 1 year posttreatment.

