- Summary statistics including the mean, the location, the location shift between the sirolimus cohort and non-sirolimus cohort, and the corresponding 95% CI (when n ≥ 3) over time and at nadir based on the Hodges-Lehmann method (Hodges & Lehmann, 1963⁵; Hodges Jr & Lehmann 1983⁶).

The nadir is defined as the lowest measurement observed between baseline through Day 30 visit post-fordadistrogene movaparvovec infusion.

No summaries will be provided by sirolimus cohort status since only one participant received sirolimus.

cTn-I:

Baseline values will be categorized as Normal (within Normal Range) and above ULN. The shifts in categories over time showing the number and percent of participants in each category will be presented.

The participants will be divided into two categories: those with baseline cTn-I \leq 99th percentile (ie, ULN) and those with baseline cTn-I > 99th percentile (ie, ULN). For Centaur assay, the cTn-I 99th percentile (ie, ULN) will be 0.03 ng/mL. The LLOQ is 0.03 and values below LLOQ will set to 0.029. For the Beckman assay, the cTn-I 99th percentile (ie, ULN) will be 19.8 ng/L. The LLOQ is 2.3 ng/L and values below LLOQ will be set to 2.29 ng/L.

For participants with baseline cTn-I > 99th percentile (ie, ULN):

- a. Count the number of post-baseline visits at which cTn-I was >3X baseline for each participant. Present the number and percentage of participants who had 0, 1, 2, or 3 visits at which cTn-I was >3X baseline.
- b. For post-baseline visits with cTn-I > 3X baseline, present descriptive summary statistics (mean, SD, median, Q1, Q3, minimum and maximum) for the maximum cTn-I level.

Graphical displays:

• Spaghetti plot including participants with ≥ 2 visit assessments post-baseline that are >3X baseline.

For participants with baseline cTn-I ≤ 99th percentile (ie, ULN),

- a. Count the number of post-baseline visits at which cTn-I was >3X 99th percentile (ie, ULN) for each participant. Present the number and percentage of participants who had 0, 1, 2, or 3 visits at which cTn-I was >3X 99th percentile (ie, ULN).
- b. For post-baseline visits with cTn-I >3X 99th percentile, present descriptive summary statistics (mean, SD, median, Q1, Q3, minimum and maximum) for the maximum cTn-I level.

Graphical displays:

• Spaghetti plot including participants with ≥ 2 visit assessments post-baseline that are $> 99^{th}$ percentile (ie, ULN).

All visits (ie, planned and unplanned) will be included in these analyses.

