6.1.4. Electrocardiograms

If more than one ECG is collected at a nominal time post-dose (for example, triplicate ECGs), the mean of the replicate measurements will be used to represent a single observation at that time point.

Absolute values and changes from baseline in QT, heart rate, QTcF, PR, RR and QRS will be summarized by dose cohort, ambulatory status at baseline, and study visit. Tables will be paged by parameter. Baseline is as defined in Section 3.1.4.

The maximum absolute value (post-dose) and the maximum increase from baseline for QT, heart rate, QTcF, PR, and QRS will be determined over all measurements taken post-dose.

The maximum increase from baseline will be calculated by first subtracting the baseline value from each post-dose measurement to give the change from baseline. The maximum of these values over the respective period will then be selected, except in the case where a participant does not show an increase. In such an instance, the minimum decrease should be taken.

Maximum increase from baseline for QT, heart rate, QTcF, PR and QRS will be summarized by dose cohort and ambulatory status.

ECG endpoints and changes from baseline (QTcF, PR and QRS) will also be summarized descriptively by dose cohort and ambulatory status at baseline using categories as defined in Appendix 1 (for QTc these correspond to ICH E14⁸). Numbers and percentages of participants meeting the categorical criteria will be provided. All planned and unplanned measurements will be counted in these categorical summaries. All values meeting the criteria of potential clinical concern will be listed.

For triplicate ECGs, if any of the three individual ECG tracings has a QTcF value \geq 500 msec, but the mean of the triplicates is not \geq 500 msec, the data from the participant's individual tracing will be described in a safety section of the CSR in order to place the \geq 500 msec value in appropriate clinical context. However, values from individual tracings within triplicate measurements that are \geq 500 msec will not be included in the categorical analysis

unless the average from the triplicate measurements is also ≥500 msec. Changes from baseline will be defined as the change between QTcF post-dose from the average of the last pre-dose triplicate values on the dosing day in each period.

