8. APPENDICES

Appendix 1. Categorical Classes for ECG of Potential Clinical Concern

Categories for QTcF

	Borderline	Prolonged	
QTcF (ms)	450≤ max. <480	480≤ max.<500	max. ≥500
QTcF (ms) increase	30≤ max. <60	max. ≥60	
from baseline			

Categories for PR and QRS

PR (ms)	max. ≥300	
PR (ms) increase from baseline	Baseline >200 and max.≥25% increase	Baseline ≤200 and max. ≥50% increase
QRS (ms)	max. ≥140	

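### SAP 6.1.3 summarises blood pressure without stated limits and without adjustment for age or height, in growing boys followed for 5 years

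*SAP*

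**What the plan says.** SAP 6.1.3 states that "Absolute values and changes from baseline in systolic and diastolic blood pressure, respiratory rate and pulse rate will be summarized by dose cohort", and also by ambulatory status and visit. Each participant's largest rise and largest fall are summarised as well. Categorical tables of post-baseline values and of maximum changes "will also be provided for the first 7 days of follow-up and the first 30 days of follow-up". The version history for the current SAP records "Section 6.1.3: Added categorical tables for the first 7" days and the first 30 days. No category limits are given.

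Protocol 9.2.1 leaves those limits to the SAP. Maximum values and changes in vital signs are to be summarised "using categories as defined in the SAP. Numbers and percentages of subjects meeting the categorical criteria will be provided", and individual values are to be listed. The only limits visible in the SAP are in Appendix 1, headed "Categorical Classes for ECG of Potential Clinical Concern", which covers QTcF, PR and QRS. Appendix 2 is not in the public text, but SAP 5.3.6 and 6.1 describe it as visit windows.

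Other safety data get more. For ECG, SAP 6.1.4 says "All values meeting the criteria of potential clinical concern will be listed". For troponin in participants with a raised baseline, SAP 6.1.2 says "Present the number and percentage of participants who had 0, 1, 2, or 3 visits at which cTn-I was >3X baseline", and there is a matching count for those with a normal baseline. SAP 6.1.2 also normalises descriptively summarised laboratory values to paediatric ranges when the normal ranges differ over time or between participants.

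The endpoint is "Abnormal and clinically relevant changes in physical and neurological examinations, weight, vital signs, ECG" and other measures through 1 year (SAP 3.1). SAP 3.2.2 and 6.2.3 carry it to 5 years.

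**The concern.** Normal blood pressure in childhood depends on age and height. A reading that is high for a 4-year-old may be ordinary for a 12-year-old, and the non-ambulatory group may include adults. Grouping by dose cohort and ambulatory status does not remove this, because the ambulatory high-dose cohort (N=16) may itself span entry ages 4 to 12. Without age- and height-specific limits, the word abnormal in the endpoint has no stated meaning for blood pressure, and no single mmHg limit would supply one.

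The setting gives reason to look. Protocol 8.4.1 anticipates steroid-related hypertension. Protocol Appendix 1 lists hypertension among events reported with the vector in the first 2 weeks. In Years 2-5 the backstop weakens: Protocol 8.1.4 limits reporting to SAEs and product-related AEs, there is no control group, and the boys continue to grow.

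**Working it through.** **Cohort sizes.** SAP 2.5 gives 3 ambulatory low-dose, 16 ambulatory high-dose and 3 non-ambulatory high-dose participants: 3 + 16 + 3 = 22, which matches the stated total.

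**Scheduled post-dose readings** (Schedule of Activities and Protocol 6.3):
- through Day 30: 6 on Days 1-2 (0.5, 1, 2, 4, 8 and 24 hours) plus Days 4, 7, 10, 14 and 30 = 11;
- rest of Year 1: Weeks 8, 12, 26 and 52 = 4, total 15;
- Years 2-5: 4 annual visits, total 19.

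The two periods named for categorical tables therefore cover 11 of 15 readings in Year 1 and 11 of 19 overall.

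**Steroid exposure after Day 30** (minimum oral doses, Protocol Section 5): 14×2 + 14×1.5 + 28×1 + 28×0.75 = 98 mg/kg over 12 weeks. By Day 30: 28 + 21 + 2 = 51. After: 47, or 48%.

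**Growth.** Assumption, not in the documents: normal systolic pressure rises 1-3 mmHg per year. Growth = rate × day/365.25.
- Day 30: 0.08-0.25 mmHg
- Day 360: 0.99-2.96 mmHg
- Day 1825: 5.0-15.0 mmHg

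At the same rate, the normal level differs by 8 × (1 to 3) = 8-24 mmHg between ages 4 and 12. A single limit has to straddle that range.

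**Noise in a mean change.** Assumption: SD of change 6-12 mmHg. Half-width = t(0.975, n-1) × SD/√n.
- n = 16: 2.131 × 6/4 = 3.2, to 2.131 × 12/4 = 6.4 mmHg
- n = 10 (if some are lost): 4.3-8.6 mmHg

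Growth is negligible at Day 30, below the half-width at 1 year, and similar to or above it at 5 years.

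**What a mean hides.** One boy rising 20-40 mmHg (illustrative) moves the mean of 16 by 20/16 to 40/16 = 1.25-2.5 mmHg.

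**How a percentile count behaves.** This bears on the remedy and does not measure a fault in the SAP. Suppose each reading has a 5% chance of exceeding the 95th percentile. The two-or-more rule here counts separate days from Day 4 on: 9 by Year 1 and 13 by Year 5.

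| Rule | Independent | Within-boy correlation 0.3-0.6 (assumed) |
|---|---|---|
| Any of 15 readings | 1 - 0.95^15 = 54% | 39% to 26% |
| Any of 19 readings | 1 - 0.95^19 = 62% | 44% to 28% |
| Two or more of 9 | 1 - 0.95^9 - 9×0.05×0.95^8 = 7% | about 10% |
| Two or more of 13 | 14% (same formula) | 15% to 14% |

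In 16 boys at 1 year, with independent readings, that is 16 × 0.537 = 8.6 chance flags for any value against 16 × 0.071 = 1.1 for two or more.

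**The case against.** A reader might infer that blood pressure is summarised only as raw values, with no counts. The documents do not support that. SAP 6.1.3 plans categorical tables, and Protocol 9.2.1 promises numbers, percentages and individual listings. What is not visible is the limits. Protocol 9.2.1 also invokes standard algorithms and reporting formats, so limits may sit in sponsor standards outside these documents. However, the version history records that references to sponsor reporting standards were removed from the SAP.

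A reader might also infer that counting stops at Day 30. That too goes beyond the text. SAP 6.1.3 offers the 7- and 30-day tables in addition to other output and takes maxima over the relevant period. SAP 6.2.3 extends the safety analysis to all 5-year data. Whole-period tables are the likelier intention, though they are not stated.

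The other side can fairly add that all AEs are collected for at least 1 year, that steroid hypertension is to be recorded as an AE, that the vector-associated hypertension falls inside the 30-day table, and that listings for 22 participants can be read one by one in a descriptive study. This limits the harm. None of it supplies a definition of pressure raised for age and height, and in Years 2-5 the AE backstop is narrower.

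**Conclusion.** The point holds as a cheap improvement. No stated summary in SAP 6.1.3 adjusts blood pressure for age or height, and no limits are given, so the plan cannot say how many boys have pressure abnormal for a child of their age and height. This matters most in Years 2-5, where assumed growth of 5-15 mmHg by Day 1825 is similar to or above the sampling noise and there is no control group.

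It would be wrong to conclude that growth distorts the 1-year primary analysis of mean change. On the same assumptions the effect is at most 0.25 mmHg at Day 30 and 1-3 mmHg at Day 360, against a half-width of 3.2-6.4 mmHg with 16 boys.

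The growth rate, SD, 5% flag rate and correlations are assumptions. The documents contain no blood-pressure norms or data, so the share of boys that raw mmHg would misclassify cannot be computed.

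**What to change.** Keep the raw tables and listings. In SAP 6.1.3, name a paediatric blood-pressure reference by sex, age and height, with adult cut-offs above its age limit, and add:

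1. Systolic and diastolic z-score change from baseline by visit.
2. n (%) at or above the 95th percentile or adult cut-off, through 7 days, 30 days, 1 year and 5 years, split by normal or abnormal baseline. Show both any value, including dosing-day readings, and two or more visits, with a note that single high values are common by chance over repeated readings.

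Both counts are needed. The any-value count keeps a single severe reading in the first 2 weeks, when hypertension has been reported with the vector. The two-visit count shows whether a rise persists.

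Use the last measured height where none is taken (Days 1-30 and Week 12). Pressure and height are already collected, so the cost is SAP wording and some programming. The drawbacks are ulnar-estimated height in some non-ambulatory participants and a general-population reference applied to short, steroid-treated boys.
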